1.1 Statement of Compliance

The trial will be conducted in accordance with International Conference on Harmonisation Good Clinical Practice (ICH GCP), and applicable United States (U.S.) Code of Federal Regulations (CFR). The Principal Investigator will assure that no deviation from funding agency and documented approval from the Institutional Review Board (IRB) will occur except where necessary to eliminate an immediate hazard(s) to the trial participants. All personnel involved in the conduct of this study have completed Human Subjects Protection and ICH GCP Training.

The protocol, informed consent form(s), recruitment materials, and all participant materials will be submitted to the IRB for review and approval. Approval of both the protocol and the consent form must be obtained before any participant is enrolled. Any amendment to the protocol will require review and approval by the IRB before the changes are implemented to the study. All changes to the consent form will be IRB approved; a determination will be made regarding whether a new consent needs to be obtained from participants who provided consent, using a previously approved consent form.

2 - Introduction

2.1 Study Rationale

The World Health Organization (WHO) has declared COVID-19, the syndrome caused by the Severe Acute Respiratory Syndrome novel Coronavirus 2 (SARS-CoV-2), a pandemic. (1) As of April 23, 2020, there are 2,658,062 cases of COVID-19, with 184,643 deaths. (2) An alarming report (3) suggested that an unmitigated epidemic will cause up to 240,000 deaths in the United States alone. So far, no reliable treatment has been found, and the most promising measures have been the non-pharmacologic measures of social distancing, handwashing, school closures, and case isolations, among others. (3)

A significant area of concern, and a potential contributing factor to the number of deaths, has been the effect of the SARS-CoV-2 on Intensive Care Unit (ICU) bed availability. Worst-case scenario analyses suggest that in the United States, 1.9 million COVID-19 patients could be admitted to the ICU, and 50% of those (960,000) would require invasive mechanical ventilation. (5) The obvious problem is that the U.S. has approximately 200,000 mechanical ventilators available, *including* the Centers for Disease Control (CDC) Strategic National Stockpile (SNS), the addition of anesthesia machines and old, retired stockpiled ventilators. (4) Also, 48% of U.S. hospitals have no intensive care unit specialists. (6)

The most common reason for ICU admission for COVID-19 patients is a respiratory failure caused by SARS-CoV-2 induced Sepsis and Acute Respiratory Distress Syndrome (ARDS). (4) While the need for a treatment for COVID-19 is urgent and the non-pharmacologic efforts to “flatten the curve” will play a significant role in reducing the burden on the US health care system, being able to slow or stop the incidents of SARS-CoV-2 induced ARDS would further reduce the pressure on health care systems. Furthermore, the success of efforts to lift the current extreme restrictions, before herd immunity is achieved or a vaccine is available, would be bolstered by having a safe, easy to implement, and effective intervention aimed at reducing the progression of conditions which lead to a high need for ICU beds and ventilators. This study proposes to use High Dose Intravenous Vitamin C (HDIVC) to stop the progression of early COVID-19 Acute Lung Injury (ALI) before it progresses to Sepsis, Acute Hypoxemic Respiratory Failure (AHRF) and ARDS. If successful, this would reduce the number of COVID-19 patients requiring endotracheal intubation, mechanical ventilation, ICU admission, and potentially offer public health benefits.

2.2 Background

In December 2019, a cluster of pneumonia cases was reported in Wuhan, China, and a novel coronavirus, SARS-CoV-2, was identified. (7) The World Health Organization (WHO) designated the respiratory disease as coronavirus disease (COVID-19) on February 12, 2020. Numerous reports have since characterized the COVID-19 clinical syndrome, ranging from asymptomatic/mild illness to severe disease leading to respiratory failure requiring mechanical ventilation (i.e., ARDS, multi-organ failure, sepsis, and death). (7 – 9) A safe, effective, and inexpensive therapy is urgently needed, one that can alter the natural course of the disease process and reduce strain on healthcare systems. High Dose Intravenous Vitamin C (HDIVC) is one such potential therapy.

Preliminary studies suggest that HDIVC is a safe and possibly effective treatment for ARDS, including ARDS of viral origin. (10) Since 1986, there has been increasing evidence that HDIVC may be useful in preventing multi-organ failure and mortality in ARDS patients. It remains unknown if HDIVC given early can halt the progression to ARDS and if it is effective in avoiding COVID-19 ARDS.

Basic Science Data to Support the Use of HDIVC in ARDS

Animal studies performed at VCU have shown that vitamin C in high doses prevents pulmonary neutrophil infiltration in murine feces-induced peritonitis (FIP) model of sepsis/ARDS (Figure 1). Vitamin C (AscA) high parenteral doses increased the clearance of bacteria from the circulation in a preclinical model of ARDS. In the same murine model of sepsis, blood was obtained using sterile technique at varying time points after induction of feces induced peritonitis with or without associated HDIVC administration. Ten μ l of blood was plated on agar plates and colonies enumerated following overnight incubation. HDIVC treated mice had a highly significant decrease in colony counts compared to untreated mice ($p < 0.01$). Bronchoalveolar lavage in these mice also demonstrated increased alveolar protein content after induction of FIP with unchanged alveolar protein content in FIP animals treated with HDIVC (data not shown), indicating that HDIVC maintained lung barrier function between the blood and the airspace. (25)

Human Trials for the use of HDIVC in Sepsis-induced ARDS

Vitamin C supplementation has been given in numerous trials for respiratory disease with mixed results (22,23).

The first study, published in 1986, compared 16 ARDS patients treated with intravenous

[figure not shown]

Figure 1. Lung pathology slides (40x magnification) of **septic** mice with fecal induced peritonitis (FIP) demonstrating Acute Lung Injury (ALI) a feature of ARDS. On the right, sections of lung (40x magnification) 16 hours after infusion of Ascorbic Acid (FIP-AscA), shows resolution of inflammation, and attenuated inflammatory cell sequestration.

vitamin C (1000 mg IV every 6 hours) plus antioxidants (N-acetylcysteine, selenium, and vitamin E) to 16 ARDS patients who received the standard care at that time (i.e., control group). There was a dramatic reduction in mortality in the vitamin C group versus the standard of care group: 37% versus 71% ($p < 0.01$). (12) A phase I trial in 2014 showed that plasma vitamin C levels in patients with severe sepsis and ARDS were low, almost at scorbutic levels (13) and that HDIVC administration had a dose-dependent effect in the prevention of multi-organ failure, as measured by the Sequential Organ Failure Assessment (SOFA) scores. (14) Patients who received a total of 200 mg/kg/day of HDIVC for 4 days (administered in 50 mg/kg/dose, every 6 hours) had significantly lower organ failure scores than patients in the placebo group. In addition, the patients in the HDIVC group (200 mg/kg/day) recovered from the scorbutic plasma levels of vitamin C, achieving plasma levels as high as 3,000 μ M on day 4.

In one study with marine recruits ($n=674$), a randomized, double-blind study of oral vitamin C at 2,000 mg/day reduced the reported pneumonia cases compared with placebo. High dose vitamin C has also been administered in a case of Enterovirus-induced ARDS in a patient who developed severe respiratory failure and required mechanical ventilation and extracorporeal membrane oxygenation (ECMO) support. Rapid improvement in oxygenation occurred early after HDIVC, which was administered for 7 days total. The patient experienced no adverse events from HDIVC or any long-term sequelae. (21)

A recent trial using the trio of vitamin C/thiamine/hydrocortisone (VITAMINS) did not show improvement in time alive or vasopressor free days in a multicenter, randomized, open-label trial. However, this trial gave a lower dose of HDIVC than we are proposing, was an open label, unblinded, and not in patients with ARDS. (15)

[figure not shown]

Figure 2. CITRIS-ALI 28 day all-cause mortality

ARDS. The statistical effect on mortality remained up to 60-days following trial completion. (11)

[figure not shown]

Figure 3. Ventilator-free days

It is important to note that none of the participants in the study developed any significant side effects from the intravenous vitamin C. The CITRIS-ALI trial results show promise for the use of HDIVC for acute respiratory failure with few significant short- or long-term side effects.

Data for the use of HDIVC in COVID-19 induced Sepsis and ARDS

High-dose Intravenous Vitamin C (HDIVC), even at much higher doses than we are suggesting in the present protocol, has been used successfully to treat COVID-19 patients in China. (18) The doses varied between 10,000 and 20,000 mg per day. (18) The authors report

The multicenter, randomized, double-blind CITRIS-ALI trial led by our lab enrolled 167 patients with ARDS who were randomized to receive 50 mg/kg of HDIVC or a placebo every 6 hours for 4 days. The treatment group showed a statistically significant difference in 28-day all-cause mortality compared to the placebo group (Figure 2), although this was a secondary outcome. (11) The 28-day mortality was 29.8% in the vitamin C group versus 46.3% in the placebo group. This can be translated as a Number Needed to Treat (NNT) of 6 patients to save one life from

In addition, the CITRIS-ALI trial (11) showed that ARDS patients who received HDIVC (at 200 mg/kg/day for 4 days, n=84) had higher ventilator-free days compared to placebo (n=83), at 13.1 days compared to 10.6 days (mean difference, 2.47; 95% CI -0.9-5.85, P=0.15). Patients treated with HDIVC also had a significant increase in ICU free days (10.7 in the vitamin C group vs. 7.7 in the placebo group (mean difference, 3.2; 95% CI, 0.3 to 5.9; P = .03).

[figure not shown]

Figure 3: Known biological effects of Vitamin C and suggested effects on COVID-19. NET: Neutrophil Extracellular Traps, TET-2 (tet methylcytosine dioxygenase 2). The methylcytosine dioxygenase that catalyzes the conversion of methylcytosine to 5-hydroxymethylcytosine. The encoded protein is involved in myelopoiesis, and defects in this gene have been associated with several myeloproliferative disorders. Vitamin C is a cofactor for TET2. This figure was created by the authors of the protocol for the purpose of the protocol (unpublished data), based

that the oxygenation index improved in all these cases in “real-time,” and all the patients were cured and discharged. Importantly, none of the patients experienced any significant side effects. (18) A randomized clinical trial is underway in Wuhan, China, to administer 12,000 mg of intravenous vitamin C every 12 hours for 7 days (significantly higher than our suggested protocol) compared with placebo. (NCT04264533) Further trials are currently in the planning and enrolling phase for HDIVC in sepsis and ARDS. Consumer groups are petitioning and urging the FDA to approve high-dose intravenous vitamin C for the COVID-19. (20) This petition has reached 17,700 signatures as of May 5th, 2020.

A summary of possible mechanisms of HDIVC for SARS-CoV-2 infection based on existing knowledge is presented in figure 3 below.

How does Vitamin C improve ARDS and Respiratory Failure in Humans?

[figure not shown]
[figure not shown]

Figure 5. Effect of Vitamin C on Human PMN

Figure 4. The endothelial glycocalyx

metalloproteinases) and exposure to reactive oxygen intermediates as occurs with acute inflammation of sepsis. Enzymatic degradation and release of cell-free DNA from activated neutrophils leads to loss of glycocalyx components (e.g., syndecan-1), which in turn leads to the display of potent adhesion receptors. This results in the sequestration of activated neutrophils and platelets in microvascular spaces amplifying vascular injury. In lung, this process produces loss of pulmonary capillary barrier function and rapid onset of alveolar injury with subsequent flooding of the alveolar space.

Figure 5 shows that neutrophils activated in vitro release cell-free DNA (Panel B). Cell-free DNA release from activated neutrophils treated with vitamin C is *completely attenuated*. (25)

In a post-hoc analysis, we used plasma obtained from patients enrolled in the multicenter, double-blind, randomized, placebo-controlled CITRIS-ALI trial. (27) Figure 6 shows that patients who received intravenous vitamin C exhibited significantly decreased 48-hour plasma cell-free DNA levels compared to placebo, and, importantly, vitamin C infusion was associated with an attenuated plasma syndecan-1 levels compared to placebo (unpublished observation). These data from CITRIS-ALI in a well-characterized patient population with sepsis-induced acute respiratory distress syndrome (ARDS) shows that increased concentrations of plasma cell-free DNA is associated with increased plasma syndecan-1 levels.

We further found that changes in both 48-hour cell-free DNA and 48-hour syndecan-1 levels predicted 28-day all-cause hospital mortality (Figure 7). In this analysis, increased syndecan-

[figure not shown]

Figure 7. Human mortality, cf-DNA and syndecan-1

measurement in septic virally infected patients may serve as a critical biomarker and possibly

The endothelial glycocalyx (Figure 4) plays an essential vasculo-protective role, modulating permeability, blood cell/vessel wall interactions, and shear stress sensing. Current research indicates the glycocalyx modulates inflammation and maintains anti-thrombogenic, anti-adhesive endothelial surfaces. Glycocalyx components such as syndecan-1 are shed by enzymatic digestion (e.g.,

1 measured at 48 hours highly correlated with worsened indices of oxygenation (data not shown). Degradation of syndecan-1 plays a vital role in early phase vascular injury, serving as a risk factor for plasma leakage. These findings have implications. Plasma syndecan-1

[figure not shown]
convey important prognostic implications of organ dysfunction produced by COVID-19 infection. Suwarto et al. found that systemic viral infection (i.e., dengue) is associated with substantial endothelial glycocalyx degradation, as evidenced by significant increases in plasma syndecan-1. (26)

These results suggest that patients could benefit from therapies targeted at protecting or restoring the glycocalyx. The data presented here strongly suggest that vitamin C's protection of the glycocalyx in septic ARDS patients led to the reduced extent of organ failure observed in CITRIS-ALI. (27) (Figure 8). The mechanisms that degrade the glycocalyx are still not

fully clarified. Still, the results of our biomarker analysis reported here more visibly point to neutrophil extracellular trap formation (i.e., cell-free DNA) as an essential factor in glycocalyx degradation. Efforts to restore the glycocalyx likely will include the stabilization of endothelial cell surface syndecan-1 expression, a vital backbone of the glycocalyx. The results of our biomarker analysis in patients from the CITRIS-ALI trial lead us to reason that intravenous infusion of vitamin C may well occupy a future role in glycocalyx

Figure 8. Vitamin C, cfDNA and syndecan-1

protection and restoration and may have a substantial role in COVID-19 infection. With the available evidence pointing to vitamin C as playing a role in glycocalyx protection, likely vitamin C's capacity both as an antioxidant and an anti-inflammatory agent is critical.

Adverse effects of High-Dose Intravenous Vitamin C

An NIH expert panel concluded that “Studies have shown that vitamin C can be safely administered to healthy volunteers or cancer patients at doses up to 1,500 mg/kg”, as per High-dose vitamin C (PDQ®)-Health professional version. (19) No safety issues were reported in the CITRIS-ALI study. (11) Another VCU study examining the use of HDIVC in patients undergoing atrial fibrillation ablation also reported no safety issues. (17)

While vitamin C infused in high concentrations does pose a potential area of concern related to **oxalate formation** and the possibility of oxalate crystal formation in the urine that may lead to renal system stone formation, no stone formation was observed during the CITRIS-ALI trial where vitamin C at 200 mg/kg per day was administered for 4 days. (17) More specifically for COVID-19, in a recent study none of the patients with COVID-19, who received high-dose intravenous vitamin C experienced any significant side effects due to the vitamin C. However, the CITRIS-ALI study did not look specifically for oxalate nephropathy, or long-term kidney outcomes in terms of AKI free-days days (18) In contrast, studies of *other* potential COVID-19 treatments have already been halted due to serious side effects. (16) **There is a clear knowledge gap in the literature in terms of the renal outcomes of high-dose, intravenous vitamin C. The highest level of evidence in terms of oxalate nephropathy and high-dose intravenous vitamin C is limited to case reports (28-30).** A recent systematic review of high-dose intravenous vitamin C, identified “identified 74 relevant articles reporting adverse events of vitamin C, but most studies did not have control or placebo group.” (31) There were nine high-quality double-blind randomized control trials (RCTs) reviewed did not show any significant adverse effects comparing to the placebo group. (31) Therefore, there is no definitive evidence that side-effects attributed to vitamin C could be from other therapies. Specific side-effects attributed to high-doses of intravenous vitamin C were “ specific adverse events attributed to high-dose IV vitamin C therapy, included “five cases of oxalate nephropathy, five cases of hypernatremia, three cases of hemolysis in patients with G6PD deficiency, two cases of glucometer error, and one case of kidney stones.” (31)

Given its success in improving outcomes for non-COVID-19 related ARDS, research suggests that HDIVC given early may also prevent the progression to ARDS in COVID-19. While treatment of COVID-19 would take priority and would not be withheld from patients with ARDS, HDIVC may provide an important therapy to reduce the burden on the US health care system. **Therefore, a proof-of-concept, phase 2 safety trial is needed.**

2.3 Risk/Benefit Assessment

2.3.1 Known Potential Risks

Potential Physical Risks of Ascorbic Acid Infusion: dry mouth, nausea, vomiting, dizziness, headache, factitious hyperglycemia (if checked with a point of care (POC) glucose testing), oxalate nephropathy, crystalluria, kidney stones and hemolysis in people with G6PD.

Potential Psychological, Social, and Legal Risks of Ascorbic Acid Infusion: No psychological, social or legal risks are identifiable from an extensive literature search.

Risks of Blood Draws: Most research data will be collected via standard of care blood draws; however, it may be necessary to do study specific blood draws when participants are enrolled and on study day 7. The risks involved in drawing blood from a vein may include, but are not limited to, momentary pain at the site of the blood draw, possible bruising, redness, and swelling around the site, bleeding at the site, feeling of lightheadedness, and very rarely, an infection at the site of the blood draw.

Since this is an ICU study, blood draws are required only if the patient does not already have an arterial or central line. If patient has one of these lines, then blood draws can be obtained through these lines without sticks. **All effort is done for all study labs to be done with AM labs and other labs that are being done for clinical care. Usually ICU patients get many**

blood draws throughout the day for other reasons. The consent 1.83 includes that patients may need up to 20 blood draws additional which will **replace the POCT glucose measurements, since POCT glucose is not reliable. Further this need to continue up to 72 hours after the last infusion to ensure that glucose measurements are accurate and minimize the risk of iatrogenic hypoglycemia.**

Risks of Peripheral Intravenous (IV) Catheter insertion: The vast majority of inpatients already have at least one peripheral IV line. In the rare occasion that an IV is not present, the study intervention requires infusion through a peripheral IV. Risk of peripheral IV insertion are exactly the same as the risk of blood draws. Risks are generally rare, since this procedure is performed hundreds of times a day in our hospital on all patients. Risk include insertion site pain, phlebitis, hematoma formation, and infusate extravasation. There are also extremely rare, but significant complications have been reported, including bloodstream and local infections, air embolization, nerve damage, arterial puncture. It is worth noting that when used as part of standard of care, peripheral IVs are inserted by the bedside nurse with just verbal consent.

Glucose Monitoring Plan:

Guidance for blood glucose monitoring in patients enrolled in the SAFE-EVICT-CORONA-ALI Trial:

Ascorbic acid is known to artifactually raise point of care (POC) blood glucose readings by all POC devices. Thus, extreme care must be taken to assure an accurate blood glucose level from a metabolic laboratory (single serum glucose, SSG) before initiating insulin therapy, including sliding scale or scheduled insulin.

Critical Care and Inpatient Unit Nursing and Treating Physician must be informed of vitamin C's effect on POC blood glucose and arterial blood gas measured glucose values. The PI(s) will instruct the ordering providers how to monitor blood glucose and insulin management in the study. Study personnel will follow each study patient closely to monitor insulin use to ensure that POC glucose screening is suspended for the research subject during the 96-hour treatment period. The following guidance for blood glucose monitoring in patients enrolled in this study will be provided to the attending staff:

- This patient is enrolled in a study with Vitamin C, which artefactually increases POC glucose testing.
- Special Order set should be used with monitoring of blood glucose.
- Use only central laboratory serum glucose quantification method via **BMP utilizing the hexokinase method and calibrated and accredited hospital analyzers.**
- Do Not Initiate or Utilize Sliding Scale, Scheduled Insulin, or Continuous Insulin Infusion without Laboratory Confirmation of Blood Glucose through the central laboratory **chemistry with BMP (hexokinase method).**
- Those receiving insulin infusion or sliding scale insulin as a part of the standard of care should have metabolic glucose screening on the schedule determined by the attending/ordering physician.
- Blood glucose monitoring for insulin administration guidance should only be by a central laboratory metabolic blood glucose results, whether or not the study patient is receiving insulin.
- **Do not use any POC device for glucose monitoring.** POC glucose testing may resume 36 hours after the last infusion of study drug.

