7.1 Discontinuation of Study Intervention

There is no defined plan to discontinue the patients from the study, however, the PI may **stop** the vitamin C infusions prematurely in the following conditions, while the other interventions will continue for safety and study reasons:

The study drug will be **stopped** without the PI completely discontinue the study assessments for the patient (i.e. the patient will still participated in blood draw assessments, blood and urine tests per protocol and documentation of outcomes):

- If the patient status improves and patient **downgrades** level of care from ICU to lower levels of care (general or stepdown).
- if participants describe symptoms of **nephrolithiasis** (kidney stones) that is flank pain and hematuria with evidence of kidney stones in the imaging studies.
- do not tolerate the drug due to side effects such as nausea, vomiting, flushing, rash, headache, or diarrhea, the PI will discontinue the study if symptoms are **CTCAE v5 grade 3** or higher and not dose reduce the study drug. In this case the FDA will also be informed.
- if a patient develops a metabolic acidosis **unexplained** by other etiologies (e.g., lactic acidosis secondary to septic shock). Determination of the presence of metabolic acidosis will be made by the clinical care team.
- Study drug will also be **stopped** if the primary care team or surrogate decision-maker requests stopping the **drug for any reasons**. Data collection will continue for these patients following the withdrawal of study drug.

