8.1.1 Venous Blood Collection Timeline

Septic patients exhibit subnormal plasma ascorbate levels. Phase I studies performed at Virginia Commonwealth University (VCU) show mean ascorbate levels of 17.5 μ M (normal human ascorbate levels 60 to 70 μ M), while some other centers report undetectable plasma vitamin C in COVID-19 patients. **Baseline ascorbate levels will be drawn, before the initiation of any infusion with subsequent trough levels for PK monitoring.**

The target plasma range for modifying pro-inflammatory biomarkers and for attenuating vascular injury was obtained from the phase I safety trial and is greater than 500 μ M as measured 24 hours after initiation of Vitamin C infusion. The day 2 – 7 plasma ascorbate levels are expected to be between 500 to 1000 μ M based on prior pharmacokinetic studies generated during the phase I trial (VCU trial was entitled: Vitamin C Infusion in Human Sepsis).

Blood drawn for ascorbate levels and biomarkers will occur at hour 0 (prior to the first infusion), **hour 48 (+ or – 3 hours as long as it is drawn prior to Infusion 9), hour 96 (+ or – 3 hours as long as it is drawn at least 3 hours post Infusion 16), and hour 168 (+ or – 6 hours).**

Schedule

	Baseline (hour 0)	Treatment days 1-4 (hour 24)	Treatment days 4-7	Days 7-14	Days 14-21	Phase 1 Study end (day 28)	Phase 2 Day 60 and Day 90
Death from ANY cause	X	X	X	X	X	X	X
Alive and Free of any	X	X	X	X	X	X	

respiratory failure							
Alive and free from invasive mechanical ventilation	X	X	X	X	X	X	
AKI (y/n) and stage	X	X	X	X	X	X	
WHO COVID-19 SCALE	X	X	X	X	X	X	X
Concomitant medication use(a)	X	X	X	X	X	X	
Plasma levels (b)	X	X	X	X	X	X	
Vital signs (c)	X	X	X	X	X	X	
Clinical assessment for kidney stone symptoms	X	X	X	X	X	X	
qSOFA score	X	X	X	X	X	X	
Ins/Outs	X	X	X	X	X	X	
Ventilator status / oxygen (e)	X	X	X	X	X	X	
Ventilator-free days	X	X	X	X	X	X	
AKI-free days	X	X	X	X	X	X	
24-hour urine collection			X5, X7	X14*	X21*	X28*	
Ventilator and drip data	X	X	X	X	X	X	
AE/tolerance (g)		X	X				
Mortality (h)	X	X	X	X	X	Date/time	
Discharge (i)	X	X	X	X	X	Date/time	
WHO COVID-19 Scale	X	X	X	X	X	X	

Footnotes:

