8.2 Safety and Other Assessments

The following data will provide the basis for assessing protocol compliance and safety as well as between-group differences in several efficacy variables. Data for each of the variables will be recorded on the days shown in the time-events schedule table. This trial will use the Common Terminology Criteria for Adverse Events version 5 (CTCAE v. 5) to assess safety and severity of symptoms.

8.2.1 Every 24 hours for as long as the patient is in the hospital: input/output, hypoglycemic events, creatinine, worst vital signs, and oxygen requirement, dialysis, admission to the ICU or need for mechanical ventilation. COVID-19 WHO ordinal status, daily serum chemistries, CBC, magnesium, telemetry ECG tracing monitoring and continuous oximetry monitoring. Patients are monitored for gastrointestinal tolerability (i.e., nausea, diarrhea) and for other adverse events (i.e., rash, headache) and agent will be **stopped** for CTCAE V5 for grade 3 or higher, while the study monitoring will continue.

8.2.2 Every, 24, 48, hours: Acute Kidney Injury-free days, Worst vital signs, Serum electrolytes, chemistries, concurrent medications AE/SAE Assessments, Weight, Bilirubin, Oxygenation Data, Kidney stone symptoms

8.2.3 Every 7, 14, 21 and 28 days: Required: Ventilator Free Days to Day 28, All-Cause Mortality to Day 28, oxygenation indices, oxygen device, use of dialysis. COVID-19 WHO ordinal status.

8.2.4 Sixty and 90 Days: All-cause mortality, routine evaluations of organ function, functional status

8.2.5 All patients will be treated **at minimum** subcutaneous unfractionated heparin for thrombo-prophylaxis (5000 units TID). Anticoagulation may be escalated by the treating physicians based on clinical and laboratory variables, such as the D-Dimer and the thromboelastogram (TEG). If suspicion of clotting arises immediate thromboelastography (TEG) will be performed to determine if clotting is ongoing. If TEG supports clotting suspicions doppler ultrasound **of the appropriate venous site** will be performed.

8.2.6 Assessment of hepatic safety: Hepatic transaminases will be monitored at baseline, day 2 and day 3 or the study. Persistent elevations will lead to: 1) discussion with ward staff, 2) will lead to right upper quadrant ultrasonography, and 3) Consultation from the Hepatology service.

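### Section 2.3.1 gives two different times after the last infusion for returning to point-of-care glucose testing (36 hours and up to 72 hours), and does not say whether the laboratory-only insulin rule then ends

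*Combined protocol and SAP*

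**What the plan says.** All the conflicting text is in the protocol's section 2.3.1, Known Potential Risks.

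- **Risks of Blood Draws.** Patients may need up to 20 additional draws in place of POC glucose, which is described as unreliable. The text continues: "Further this need to continue up to 72 hours after the last infusion to ensure that glucose measurements are accurate". It adds the aim of limiting iatrogenic hypoglycemia.
- **Glucose Monitoring Plan, staff guidance, last bullet.** "POC glucose testing may resume 36 hours after the last infusion of study drug".
- **Glucose Monitoring Plan, staff guidance, insulin bullets.** One reads "Do Not Initiate or Utilize Sliding Scale, Scheduled Insulin, or Continuous Insulin Infusion without Laboratory Confirmation of Blood Glucose". Another reads "Blood glucose monitoring for insulin administration guidance should only be by a central laboratory metabolic blood glucose results". Neither has an end time.
- **Glucose Monitoring Plan, study personnel.** They follow patients to "ensure that POC glucose screening is suspended for the research subject during the 96-hour treatment period". No duty after the infusions is stated.

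Two other sections bear on timing. Section 7.1 allows the drug to be stopped early, for example when a patient moves down in "level of care from ICU to lower levels of care (general or stepdown"). Section 8.1.1 says that on days 2 to 7 "plasma ascorbate levels are expected to be between 500 to 1000" μM, against a normal range of 60 to 70 μM.

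**The concern.** The protocol itself names the hazard: a falsely high POC reading can lead to insulin that the patient does not need. The time at which POC testing becomes acceptable again is therefore a safety instruction, and it should have one value. Between 36 and 72 hours after the last infusion, the staff guidance permits POC testing while the risk text still requires laboratory glucose for accuracy.

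The conflict matters in either direction. If the longer interval is needed, the staff guidance brings back readings that the risk text does not trust. If the shorter one is enough, the risk text prolongs laboratory draws by up to 36 hours without need.

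The open-ended insulin bullets add a second ambiguity. Once POC testing resumes, a clinician could take the laboratory-only rule as still in force or as having lapsed with the suspension. The text supports either reading.

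Hypoglycemia is collected but is not a listed endpoint, so no bias in the listed outcomes is claimed.

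**Working it through.** The plan gives no figure to reproduce. The check compares the texts and places them on the study clock.

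**Inputs**
- 36 hours after the last infusion: section 2.3.1, staff guidance.
- Up to 72 hours after the last infusion: section 2.3.1, Risks of Blood Draws.
- Personnel check over the 96-hour treatment period: section 2.3.1, Glucose Monitoring Plan.
- Sixteen 30-minute infusions, one every 6 hours: sections 4.1 and 6.1.1.
- Maximum 60 patients, 30 per arm: Synopsis and section 9.

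**Comparison of the texts.** Both intervals start at the last infusion and both bear on when POC glucose can be relied on. The risk text refers to consent 1.83, which matches the current protocol version, so it cannot be set aside as a leftover. No other section links the two figures.

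**Clock times.** Infusion k starts at 6(k − 1) hours after Dose 1 starts and ends at 6(k − 1) + 0.5 hours.

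| Last infusion given | Ends (h) | + 36 h | + 72 h | Width of conflict |
|---|---|---|---|---|
| k = 16 (full course) | 90.5 | 126.5 | 162.5 | 36 h |
| k = 1 (earliest stop) | 0.5 | 36.5 | 72.5 | 36 h |

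The width is 72 − 36 = 36 hours for every k. Early stopping under section 7.1 moves the window earlier but does not shorten it. After a full course the window is 126.5/24 = 5.3 to 162.5/24 = 6.8 days. That lies within the day 2 to 7 period in section 8.1.1, but no section gives an ascorbate level below which POC readings become usable.

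**Reach of the personnel check.** If the 96 hours run from Dose 1, the check after a full course covers 96 − 90.5 = 5.5 hours of either post-infusion interval. If the 96 hours also run regardless of early stopping, which the text does not say:
- all 36 hours are covered only if 6(k − 1) + 36.5 ≤ 96, so k ≤ 10 (k = 10 gives 90.5 h; k = 11 gives 96.5 h);
- all 72 hours are covered only if 6(k − 1) + 72.5 ≤ 96, so k ≤ 4 (k = 4 gives 90.5 h; k = 5 gives 96.5 h).

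**Patients concerned.** At most 60 come under the guidance, because treatment is blinded. At most 30 receive ascorbic acid and can show the artefact. The number still in hospital, glucose-monitored and on insulin in the window is not given and cannot be derived.

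**The case against.** The strongest reply is that 72 hours is a ceiling. The sentence sits in a description of blood-draw burden, next to another maximum (20 draws), and a disclosed maximum is compatible with permission to resume POC testing at 36 hours. On this view the staff list is the only operating instruction, and it contains one interval. This reading is possible, but it does not remove the problem. The sentence says that the laboratory measurements need to continue and gives accuracy as the reason, which concerns the assay rather than the burden. Even as a ceiling, it comes with no criterion for stopping between 36 and 72 hours.

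Second, the insulin bullets, read literally, still bar POC-guided insulin after 36 hours. This stands, and it is why the harm is put as possible only. The text does not say that those bullets outlast the suspension.

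Third, the burden of extra draws is softened: section 2.3.1 caps them, lets existing arterial or central lines be used, and combines study samples with clinical ones. This also stands, and it makes the cost of an unnecessarily long interval smaller.

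Fourth, the personnel check never claimed to enforce a post-infusion interval, and the plan has other controls, namely instruction of ordering providers and a special order set. That is fair. The check is a monitoring duty and not a third end time. It is relevant only because, after a full course, it enforces neither interval to its end.

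**Conclusion.** The concern holds. Section 2.3.1 contains a contradictory safety instruction: two post-infusion intervals that differ by 36 hours, with nothing to reconcile them, and a laboratory-only insulin rule whose end is not stated. The 36-hour width does not depend on when the drug stops. The clock times of 126.5 and 162.5 hours assume that all 16 infusions are given on schedule.

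The documents do not show which interval is adequate, and the expected ascorbate levels in section 8.1.1 do not settle it. Whether any patient would receive insulin on a false reading is also unknown; the upper bounds are 60 patients under the guidance and 30 exposed to the artefact. The point should be fixed because it concerns patient safety and is cheap to correct. It does not affect the analysis of the listed outcomes.

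**What to change.** The sponsor should reconcile the blood-draw risk text, the staff guidance and the personnel check in section 2.3.1 so that they give one post-infusion interval with its basis. The special order set and the consent form, which could not be seen for this review, should be checked and brought into line. The text should also state whether the laboratory-only insulin rule ends with that interval or continues beyond it. No interval is proposed here; that is a clinical decision for the sponsor.

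No change to the capture of hypoglycemia is needed. Section 8.2.1 already requires it ("Every 24 hours for as long as the patient is in the hospital: input/output, hypoglycemic events"), and the Schedule of Activities carries it through Day 22-28.

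The cost is a wording correction in three places in section 2.3.1 and alignment of the two related documents. If the personnel check is extended past the treatment period, that adds a short monitoring duty. Sample size, visits and data collection do not change.
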